5.2.2. Nominal Timepoints

Visit windows will apply per Appendix 3. Analysis Windows for Reporting.

Note that NaF-1 and NaF-2 are scheduled for baseline and week 13, respectively. NaF-3, however, is more fluid and can occur depending on different disease progressions or 2-years of therapy, per Section 3.1. If NaF-3 occurs before the scheduled NaF-2, then that scan will be NaF-3, and the pre-planned NaF-2 will not exist.

For endpoints only collected once post-baseline at NaF-3 (eg, circulating tumor cells), the NaF-3 slotted value will be the measurement closest to the NaF-3 scan.

5.2.3. Definition of Study Day

The study day for assessments occurring on or after the first dose of study treatment (eg, adverse event onset, tumor measurement) will be calculated as:

Study day = Date of the assessment/event - start date of study treatment +1.

The study day for assessments occurring prior to the first dose of study treatment (eg, baseline characteristics, medical history) will be negative and calculated as:

Study day = Date of the assessment/event – start date of study treatment.

The study day will be displayed in all relevant data listings.

5.2.4. Unscheduled Assessments

Unscheduled assessments will be used when deriving baseline and worst case on-treatment for safety and patient-reported outcome analyses (except where noted for baseline ECGs). Additionally, unscheduled assessments will be used for efficacy analyses (eg, defining date of PSA progression, date of last contact).

5.2.5. Standard Derivations and Reporting Conventions

The following conversion factors will be used to convert days into weeks, months or years: 1 week = 7 days, 1 month = 30.4375 days, 1 year = 365.25 days.

Percentages will be reported to one decimal place. The rounding will be performed to closest integer / first decimal using the common mid-point between the two consecutive values. Eg, 5.1 to 5.4 will be rounded to an integer of 5, and 5.5 to 5.9 will be rounded to an integer of 6.

5.2.6. Analyses for Categorical Data

The number and percentage of patients in each category will be provided for categorical variables. Unless otherwise specified, the calculation of proportions will include the missing category. Therefore counts of missing observations will be included in the denominator and presented as a separate category.

In case the analysis refers only to certain visits, percentages will be based on the number of patients with an assessment at that visit, unless otherwise specified.

If a binary proportion requires a confidence interval, it will be calculated with a 2-sided exact 95% CI using the Clopper-Pearson method (Clopper, C. J.; Pearson, E. S. (1934)). This confidence interval is an exact interval, not relying on any normal approximations. Sample SAS code can be found in Appendix 2. Sample SAS Code.

5.2.7. Analyses for Continuous Data

Descriptive statistics, including the number of observations (N), mean, standard deviation, median, minimum, 25th quantile, 75th quantile, and maximum values, will be provided for continuous variables.

In case the analysis refers only to certain visits, descriptive statistics will be based on the number of patients with a non-missing assessment at that visit, unless otherwise specified.

5.2.8. Analysis of Covariance

A linear model for analysis of covariance (ANCOVA) will be used to analyze continuous data collected at baseline and at particular post-baseline visits. The dependent variable in the ANCOVA model will be the change from baseline at the specified post-baseline windowed visit. The model will include fixed effects terms for:

- Treatment (as a categorical variable);
- Baseline value (as a continuous variable);
- Study site (as a categorical variable).

The observed margins option (OM) will be implemented in assigning categorical weights when calculating the least squares means. There will be no imputation for missing data in the analyses. While there is only one treatment arm in this study, the inclusion of the fixed effect for treatment is needed in order to produce the desired least squares mean.

The model-adjusted mean change from baseline will be presented at the specified postbaseline visit using the least squares mean, its standard error, and its 95% confidence interval.

In the event of convergence problems, then the fixed effect term for study site will be removed and the model re-run.

Sample SAS code for the ANCOVA model is found in Appendix 2. Sample SAS Code.

5.2.9. Analysis for Log-Transformed Data

Endpoints that are markedly skewed can be analyzed with log-transformation. The natural log of the baseline and the natural log of post-baseline observed data will be used in the ANCOVA analysis from Section 5.2.8. Nominal change in the log-transformed data (log[post-baseline value] minus log[baseline value]) will be analyzed. The following will estimate a percent change from baseline and will be displayed in the tables.

Percent change for treatment = $[\exp(LSMean) - 1]*100\%$

Likewise, the confidence intervals for the percent change will be obtained similarly, where the above back-transformation is applied to the log-transformed confidence interval for the LSMean. If any values for analysis are zero, then a positive value of 0.0001 will be used instead; this will allow the computation of the natural log.

5.3. Methods to Manage Missing Data

Missing data will not be imputed unless specified elsewhere in the SAP. Missing dates or partially missing dates will be imputed conservatively for adverse events and prior/concomitant medications/procedures. Specific rules for handling missing or partially missing dates for date of birth, adverse events, prior/concomitant medications/procedures, and diagnosis of cancer are provided in Appendix 1. Imputation of Missing/Partially Missing Dates. Any imputations will occur at the analysis dataset level and not the raw dataset level. Additionally, in all patient data listings imputed values will be presented and flagged as imputed.

Missing statistics, eg, when they cannot be calculated, should be presented as 'ND' for not done, 'NR' for not reached or 'NA' for not applicable. For example, if N=1, the measure of variability cannot be computed and should be presented as 'ND' or 'NA'. If too few events are observed in the KM analyses, then certain quartiles may not be estimable; hence NR should be presented.

Missing toxicity grades for adverse events:

Prior to Study Treatment: If no toxicity grade is available or the grade is reported as unknown for an adverse event prior to the first study treatment, then Grade 1 will be assumed for purposes of defining a baseline grade for assessing if further occurrences are treatment emergent. However, if the patient experiences multiple episodes of the same AE prior to study treatment, then the maximum toxicity grade observed prior to study treatment will be utilized in assessing if further occurrences are treatment emergent.

During Study Treatment: If no toxicity grade is available or the grade is reported as unknown for an adverse event during the study treatment, then the event will be considered treatment emergent unless a baseline event was reported as Grade 4.

In summaries which present maximum toxicity grade, the maximum of non-missing grades will be displayed. Missing grade will only be displayed for cases where a patient reported only one event and the grade is missing.

For incomplete day of last dose of study drug, the 15th of the month will be assumed in determining the treatment-emergent period.

6. ANALYSES AND SUMMARIES

All efficacy analyses will be based on the AT population. Any confidence intervals presented will be 2-sided 95% CI. No adjustments to the confidence intervals are planned for any multiple testing. The start day for time to event analyses will begin at the date of first study drug.

Safety analyses (adverse events, laboratory tests, etc.) will be based on the AT population.

A grid-summary of the efficacy analyses can be found in Appendix 4. Summary of Efficacy Analyses.

6.1. Primary Endpoint

The primary endpoint is the proportion of patients with ≥ 1 responding bone lesions at NaF-3. A lesion is considered responding if the change from baseline at NaF-3 in total standardized uptake value (SUV(total)) is below the limit of agreement (LOA).

The primary endpoint will be summarized with number and percent of patients with >1 responding bone lesions at NaF-3 along with the 95% CI using the Clopper-Pearson method

[figure not shown]
This endpoint will be analyzed for all patients in the AT population who also have non-missing scans at both NaF-1 and NaF-3. Patients not having both NaF-1 and NaF-3 will be counted as non-evaluable (hence not included in the denominator of the point estimate).

[figure not shown]

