10.3.1 Primary Efficacy Endpoint Analysis

The primary efficacy endpoint is the proportion of patients with at least 1 responding bone lesion (defined as a lesion with an SUV_{total} less than at baseline) on the third ¹⁸F-NaF PET/CT scan (NaF-3) performed for each patient. This assessment will be triggered by any of the following events:

- PSA progression (an increase of at least 25% AND an absolute increase of at least 2.0 ng/mL above nadir)
- Bone disease progression (the appearance of at least 2 new lesions after screening assessed by ^{99m}Tc-MDP bone scintigraphy)
- Soft tissue disease progression defined by RECIST 1.1⁷
- Clinically relevant progression (eg, significant bone pain or a skeletal-related event)
- At 2 years without progression after treatment initiation

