10.6 Determination of Sample Size

The total number of patients to be included in this study is approximately 20 and is based on practical clinical considerations.

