3.1. Primary Endpoint

The single primary endpoint is the **proportion of patients with** \geq 1 **responding bone lesion on the third scheduled F-NaF PET/CT scan** for this study. For clarity going forward, this scan will be referred to as NaF. Three such NaF scans are scheduled and are noted below:

| Scan identifier | Scheduled to occur at |
|-----------------|--|
| NaF-1 | Screening |
| NaF-2 | Week 13 |
| NaF-3 | Time of progression, or at 2 years after |
| | treatment start, whichever occurs first* |

* If progression occurs before Week 13, then NaF-3 will constitute the scan at progression and support the primary analysis, even though NaF-2 hadn't occurred yet.

A lesion is considered responding if the change from baseline in total standardized uptake value (SUV(total)) is below the limit of agreement (LOA). The LOA will be estimated based upon test/retest analysis and provided by the vendor.

Protocol MDV3100-18 (C3431012) (Enzalutamide) Statistical Analysis Plan

The NaF-3 will be triggered by the earliest of any of the following events:

- Prostate-specific antigen (PSA) progression:
 - Defined as percentage change from baseline $\geq 25\%$ and nominal increase ≥ 2.0 ng/mL above the nadir (or above the baseline if no decline by week 13).
- Bone disease progression:
 - Defined as ≥ 2 new lesions assessed by bone scintigraphy.
- Soft tissue disease progression:
 - Defined by RECIST v1.1.
- Clinically relevant progression:
 - Defined by the investigator.
- Two years after start of therapy.

[figure not shown]
NaF scans will be interpreted by a central imaging vendor.

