Appendix 3. Analysis Windows for Reporting

The below applies to certain windowed summaries and analyses (eg, descriptive statistics by visit, change from baseline by visit, etc.). Windows will be based on the patient's date of first dose of study medication; the first day of dosing is Day 1.

Adverse events, however, do not follow windows.

If there is more than one observation in a specific window, then the one closest to the target day will be selected for analysis. If there are two observations that are equidistant to the target day, then the first of these two observations will be selected for analysis. If there are two or more observations on the same selected day within the same analysis window, then the mean of these observations will be used.

| Week | Target Day | Analysis Window |
|----------|------------|----------------------|
| Week 5 | 29 | Day 2 to Day 57 |
| Week 13 | 85 | Day 58 to Day 113 |
| Week 21 | 141 | Day 114 to Day 169 |
| Week 29 | 197 | Day 170 to Day 225 |
| Week 37 | 253 | Day 226 to Day 281 |
| Week 45 | 309 | Day 282 to Day 337 |
| Week 53 | 365 | Day 338 to Day 393 |
| Week 61 | 421 | Day 394 to Day 449 |
| Week 69 | 477 | Day 450 to Day 505 |
| Week 77 | 533 | Day 506 to Day 561 |
| Week 85 | 589 | Day 562 to Day 617 |
| Week 93 | 645 | Day 618 to Day 673 |
| Week 101 | 701 | Day 674 to Day 729 |
| Week 109 | 757 | Day 730 to Day 785 |
| Week 117 | 813 | Day 786 to Day 841 |
| Week 125 | 869 | Day 842 to Day 897 |
| Week 133 | 925 | Day 898 to Day 953 |
| Week 141 | 981 | Day 954 to Day 1009 |
| Week 149 | 1037 | Day 1010 to Day 1065 |
| Week 157 | 1093 | ≥ Day 1066 |

Additional weeks if needed are derived by adding 8 weeks onto Week, and adding 56 days onto Target Day. Lower and upper bounds are also adjusted by adding 56 days.

| Endpoint | Classificati on | Population | Descriptive analysis | Inferential analysis |
|-------------------|--------------------|------------|--------------------------------|-----------------------------|
| Proportion with | Primary | AT* | Number and % | Point estimate and |
| responding bone | 5 | | | CI using Clopper- |
| lesions at NaF-3 | | | | Pearson method |
| | | | | |
| Heterogeneity of | Secondary | AT* | Summary stats | |
| response at NaF-3 | | | and histograms | |
| | | | | |
| CCI | | | | |
| | | | | |
| | | | | |
| | | | | |
| | | | | |
| | | | | |
| | | | | |
| | | | | |
| | | | | |
| | | | | |
| | | | | |
| | | | | |
| | | | | |
| | | | | |
| | | | | |
| | | | | |

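### SAP 6.1 tabulates patients with >1 responding bone lesion although the primary endpoint is at least 1; read literally, the reported proportion would be lower than or equal to the declared one (check the source PDF)

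*SAP*

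**What the plan says.** Protocol 10.3.1 states: "The primary efficacy endpoint is the proportion of patients with at least 1 responding bone lesion". The protocol synopsis and Sections 1.1, 3.1 and 3.5 use the same threshold. SAP 3.1 also defines the endpoint with a greater-than-or-equal sign before the number 1.

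SAP 6.1 begins consistently: "The primary endpoint is the proportion of patients with ≥ 1 responding bone lesions at NaF-3". Its next paragraph says how that endpoint is to be summarised, with a 95% Clopper-Pearson interval, and there the quantity is the "number and percent of patients with >1 responding bone lesions at NaF-3".

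Two other places could have settled the threshold, but neither does. The efficacy summary grid (SAP Appendix 4) names the primary endpoint as the proportion with responding bone lesions and gives no count. The Clopper-Pearson sample code in SAP Appendix 2 takes a 0/1 variable called RESPONSE and does not say how it is derived.

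**The concern.** The count of responding lesions is the patient-level response threshold. The paragraph carrying >1 is the one from which the primary table would be programmed. Taken at its word, it requires two or more responding lesions and moves every patient with exactly one from responder to non-responder. The denominator is unchanged, because it depends only on having both NaF-1 and NaF-3.

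Such patients are plausible in this design. Protocol 4.1 requires only two lesions on bone scintigraphy. Protocol 3.5 explains that requirement partly by the wish to show discordant responses among one patient's lesions. SAP 5.1 sets no formal hypothesis and makes estimation the aim, so this proportion and its interval are the main result of the study.

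**Working it through.** **Is there a figure to reproduce?** No. The documents state no expected proportion, precision or power, and Protocol 10.6 says: "The total number of patients to be included in this study is approximately 20 and is based on practical clinical considerations".

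**Step 1: the identity.** For any data set, n(>1) = n(≥1) − n(exactly 1). The >1 proportion can never exceed the ≥1 proportion. The two are equal when no evaluable patient has exactly one responding lesion.

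**Step 2: effect per patient.** With 20 evaluable patients, each patient with exactly one responding lesion moves the estimate by 1/20 = 5.0 points. With 16 evaluable the step is 1/16 = 6.25 points.

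**Step 3: effect on the interval.** The exact limits are the beta quantiles B(0.025; x, n−x+1) and B(0.975; x+1, n−x). Assume, for illustration, 20 evaluable patients of whom 18 have at least one responding lesion:

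| Patients with exactly one | Reported under >1 | 95% CI |
|---|---|---|
| 0 | 18/20 = 90.0% | 68.3 to 98.8 |
| 1 | 17/20 = 85.0% | 62.1 to 96.8 |
| 2 | 16/20 = 80.0% | 56.3 to 94.3 |
| 4 | 14/20 = 70.0% | 45.7 to 88.1 |

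The first row is also the result under the declared endpoint.

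**Step 4: how large the gap could be.** The number of lesions per patient (m) and the response probability per lesion (q) are not in the documents. Nor is the lesion-level cut-off, since SAP 3.1 says: "The LOA will be estimated based upon test/retest analysis and provided by the vendor". Both m and q are therefore assumptions. If lesions respond independently, P(≥1) = 1 − (1−q)^m and the gap is P(exactly 1) = m·q·(1−q)^(m−1).

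| m | q | P(≥1) | P(>1) | Gap (points) |
|---|---|---|---|---|
| 2 | 0.5 | 75.0% | 25.0% | 50 |
| 5 | 0.3 | 83.2% | 47.2% | 36 |
| 10 | 0.1 | 65.1% | 26.4% | 38.7 |
| 10 | 0.3 | 97.2% | 85.1% | 12.1 |
| 10 | 0.5 | 99.9% | 98.9% | 1.0 |
| 20 | 0.1 | 87.8% | 60.8% | 27.0 |
| 20 | 0.5 or more | about 100% | about 100% | about 0 |

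As a check on one row: for m = 5 and q = 0.3, 5 × 0.3 × 0.7⁴ = 1.5 × 0.2401 = 0.360.

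**Step 5: correlation within a patient.** For two lesions with correlation ρ, the gap is 2q(1−q)(1−ρ). At q = 0.5 it is 0.5 × (1−ρ): 50 points at ρ = 0, 25 points at ρ = 0.5 and none at ρ = 1. Positive correlation therefore shrinks the two-lesion figure.

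**The case against.** The strongest reply is that this is a single character whose meaning nobody would mistake. The disputed sentence says it summarises the primary endpoint, which the paragraph above defines as at least one. Every other statement of the threshold agrees. SAP Section 2 says a major change to the primary endpoint or its analysis would also appear in a protocol amendment, and Amendment 2, on which this SAP is based, keeps at least 1. A reader might infer that the sponsor raised the threshold to two lesions; the documents do not support that. This reply stands as to intent. It does not correct the sentence that specifies the table, and neither appendix restates the rule.

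A second reply is that the sign may have been lost when the PDF was converted to text. The conversion kept the greater-than-or-equal sign in the preceding paragraph. But in SAP 6.5.5 it appears to have dropped a minus sign from the treatment-duration formula while keeping the one in the capsule formula, so one correct symbol does not vouch for the next. The text alone cannot settle this, and the point is conditional on the source PDF.

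A third reply is that the large gaps belong to few lesions. Two lesions is the entry minimum on scintigraphy, and Protocol 1.1 calls NaF PET/CT the more sensitive method, so counts on NaF may be higher. That is fair, and it is why the range in the working runs down to about zero. More lesions do not by themselves remove the gap, however: at a 10% response rate per lesion it is still 27 points with 20 lesions.

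**Conclusion.** Subject to the source PDF, SAP 6.1 is wrong as written: its tabulation sentence contradicts its own definition, SAP 3.1 and the protocol. It is most likely a slip rather than a chosen analysis, but it sits in the instruction for the primary estimate and should be corrected before programming.

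A reader might infer that the literal wording must give a lower proportion, perhaps by tens of points. The documents do not support that. The proportion would be lower or equal, and the gap is exactly the share of evaluable patients with one responding lesion. That is 5 points per such patient if all of the approximately 20 are evaluable, and nothing if there are none. The model-based gaps, from 50 points to about 0, rest on assumed lesion counts, assumed response rates and independence between lesions. None of these comes from the documents.

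No sample size, power or decision rule depends on the symbol.

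**What to change.** Check the source PDF of SAP 6.1. If it reads >1, replace it with at least 1, in words, so that no symbol can be lost or misread. In SAP Appendix 2, define RESPONSE = 1 as at least one responding bone lesion at NaF-3 and RESPONSE = 0 as none, among patients with both NaF-1 and NaF-3. The RESPONSE definition is worth adding even if the PDF proves correct, because the sample code currently leaves the derivation open.

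The cost is a few words in the SAP. The protocol needs no amendment, because it already states the intended threshold.

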6.2. Secondary Endpoint(s)

[figure not shown]
The secondary endpoint is the observed heterogeneity of response across all bone lesions, SUV(hetero). This endpoint will be assessed for each patient when their primary endpoint is assessed, and is based on the post-baseline scan NaF-3. This endpoint was analyzed at the central vendor and provided to the sponsor. Summary statistics will be used to describe the endpoint. Graphical displays utilizing histograms will also be produced.

This endpoint will be analyzed for all patients in the AT population who also have nonmissing scans at both NaF-1 and NaF-3.

[figure not shown]

[figure not shown]

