2.2 Secondary Objective

- Evaluate heterogeneity of response in metastatic bone lesions at the time the primary objective is assessed

CCI

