2.1. Study Objectives

Primary Objectives:

• To evaluate F-NaF PET/CT imaging as a method for assessing treatment response in metastatic bone lesions either at time of disease progression, or after 2 years of treatment, whichever comes first.

Secondary Objectives:

• To evaluate the heterogeneity of response in metastatic bone lesions at the time the primary objective is assessed.

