3. ENDPOINTS AND BASELINE VARIABLES: DEFINITIONS AND CONVENTIONS

Standardized uptake value (SUV) is a unitless measure derived from the imaging PET/CT scans as a ratio of image-radioactivity concentration to the whole-body concentration. SUV and its various uptake measures described below will be analyzed at the central vendor and provided to the sponsor.

For a particular lesion (n), where n = 1, 2, 3, ... N, a 3-dimensional volume of interest (VOI) will be analyzed. Within that VOI for that lesion, there are numerous voxels which compromise the volume. These voxels are 3-dimensional analogs of the 2-dimensional pixels. A particular voxel will be voxel (k), and there are K voxels compromising the entire VOI for that lesion, where k = 1, 2, 3, ... K. Let SUV_k be the SUV for a voxel (k) within that particular lesion.

- **SUV(total)** is the total standardized uptake value. This measure assesses the total tumor burden.
 - First, each lesion (n) of interest produces its own SUV(total) by summing from k=1 to k=K of SUV_k.
 - Second, the sum from n=1 to n=N of each lesion's SUV(total) will produce the desired SUV(total).

- SUV(mean) is the mean standardized uptake value.
 - First, each lesion (n) of interest produces its own SUV(mean) by summing from k=1 to k=K of SUV_k and then dividing that sum by K.
 - Second, the mean from n=1 to n=N of each lesion's SUV(mean) will produce the desired SUV(mean).
- SUV(max) is the maximum standardized uptake value.
 - First, each lesion (n) of interest produces its own SUV(max) by taking the maximum value from k=1 to k=K of SUV_k.
 - Second, the maximum from n=1 to n=N of each lesion's SUV(max) will produce the desired SUV(max).
- **SUV(hetero)** is the heterogeneity measure of tumor activity across all lesions
 - First, each lesion (n) of interest produces its own SUV(mean) by summing from k=1 to k=K of SUV_k and then dividing that sum by K.
 - Second, that lesion's mean is subtracted from the SUV(mean) above, and that difference is then squared.
 - Third, those squared differences from n=1 to n=N are then summed, and then divided by N to produce the desired **SUV(hetero)**.

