3.2. Secondary Endpoints

[figure not shown]
There is one secondary endpoint for this study, namely **the heterogeneity of response across all bone lesions at the time the primary endpoint is assessed, SUV(hetero)**. At the NaF-3, the observed SUV(hetero) will be assessed.

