3.4. Baseline Variables

The date of first dose (start date) of study treatment is the earliest date of non-zero dosing of the study drug. The date of last dose of study treatment is the latest date of non-zero dosing of the study drug.

No windowing will be applied when defining baseline. Any deviations from the protocol specified window will be documented as protocol deviations. For efficacy analyses and baseline characteristics associated with tumor assessments, the last assessment prior to the date and time of first study drug will serve as the baseline assessment.

For safety, the last assessment performed on or prior to date of the first dose of study treatment will serve as the baseline assessment. If there are no observations meeting these criteria, then baseline is considered missing.

Post-baseline value is defined as a measurement taken after the first administration of study drug. Change from baseline is defined as (post baseline value – baseline value). Percent change from baseline is defined as [(post baseline value – baseline value)/(baseline value)] multiplied by 100%. Both date and time of study drug administration and measurement will be considered when calculating baseline value. If time is not available, then date only will be used.

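### The only secondary endpoint measures the spread of lesion uptake on one scan, so by itself it cannot isolate heterogeneity of response

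*SAP*

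**What the plan says.** **Objective.** Protocol section 2.2: "Evaluate heterogeneity of response in metastatic bone lesions at the time the primary objective is assessed". SAP section 2.1 repeats it: "To evaluate the heterogeneity of response in metastatic bone lesions at the time the primary objective is assessed".

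**Endpoint.** SAP section 3.2 names one secondary endpoint, under the label of heterogeneity of response, and specifies: "At the NaF-3, the observed SUV(hetero) will be assessed". Section 6.2 adds: "This endpoint will be assessed for each patient when their primary endpoint is assessed, and is based on the post-baseline scan NaF-3". The output is summary statistics and histograms.

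**Formula.** SAP section 3 takes each lesion's SUVmean, subtracts it from the mean over lesions and squares the difference. It ends: "Third, those squared differences from n=1 to n=N are then summed, and then divided by N to produce the desired" SUV(hetero). Protocol section 10.3.2 gives the same formula. Every term comes from one scan. Protocol Table 14 describes the measure as heterogeneity of uptake and of lesion activity, not of response.

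**What response means elsewhere.** SAP section 3.1: "A lesion is considered responding if the change from baseline in total standardized uptake value (SUV(total)) is below the limit of agreement (LOA". Protocol section 10.3.1 also compares lesion SUV(total) with its baseline value. SAP section 3.4 begins its general rule "Change from baseline is defined as (post baseline value" and then subtracts the baseline value. Protocol section 3.5 explains that at least two lesions are required so that discordant treatment response between a patient's lesions over time can be shown, with each patient as his own control.

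**Analysis set.** SAP section 6.2: "This endpoint will be analyzed for all patients in the AT population who also have nonmissing scans at both NaF-1 and NaF-3".

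**The concern.** The objective is about how differently a patient's lesions changed under enzalutamide. The endpoint describes how different the lesions look at NaF-3. These coincide only if the lesions looked alike before treatment. Where they did not, part or all of the NaF-3 spread may be carried over from baseline, and a response that brings unequal lesions closer together lowers the score.

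The NaF-3 summaries and histograms would be reported as heterogeneity of response. A reader could then take a high value as discordant response and a low value as uniform response, and neither inference follows from the score alone.

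**Working it through.** The plan gives no numerical figure to reproduce: the endpoint is descriptive, and the sample size of about 20 rests on practical considerations (Protocol section 10.6, SAP section 5.1). The check applies the plan's own formula to assumed lesions.

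**Inputs.** The formula is from SAP section 3: SUV(hetero) = sum of (lesion SUVmean - mean of lesion SUVmeans)² / N. Because the SAP defines the global mean as the unweighted mean of the lesion means, this is exactly a variance with divisor N. The protocol does not say how its global mean is weighted; with another weighting the score would be a mean squared deviation about a different centre, still from one scan. The lesion values below are assumptions, with three matched lesions of equal and constant volume, so that percentage change in SUVmean equals percentage change in SUV(total).

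| Case | NaF-1 to NaF-3 | Score NaF-1 | Score NaF-3 | SD of absolute change | SD of log ratio |
|---|---|---|---|---|---|
| A | 10/20/30 to 5/10/15 | 66.7 | 16.7 | 5 | 0 |
| B | 10/20/30 unchanged | 66.7 | 66.7 | 0 | 0 |
| C | 10/20/30 to 20/20/20 | 66.7 | 0 | 10 | 0.556 |
| D | 20/20/20 to 10/20/30 | 0 | 66.7 | 10 | 0.556 |
| E | 15/10/5 to 5/10/15 | 16.7 | 16.7 | 10 | 1.099 |

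The SDs use divisor n-1. Worked examples:

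- B, score: (100 + 0 + 100)/3 = 66.7, although nothing changed.
- C, score: all deviations are 0, so the score is 0. The changes are +10, 0, -10 (+100%, 0%, -33%), with SD 10. The log ratios are 0.693, 0, -0.405, with SD 0.556.
- E: the changes are -66.7%, 0%, +200%. The log ratios are -ln 3, 0, ln 3, with SD ln 3 = 1.099.

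**What this shows.** B and D have the same NaF-3 score, yet B has no response in any lesion and D has one lesion halved and another up by 50%. C has the lowest possible score and the same spread of change as D. The failure in B and C appears on both the absolute and the log scale. Case A misleads on neither scale taken alone: its score of 16.7 equals the variance of its absolute changes, and its log-scale spread is 0.

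**Why.** For matched lesions, write d for change and b for the NaF-1 value. Then NaF-3 variance = Var(b) + Var(d) + 2 Cov(b, d). Response heterogeneity on the absolute scale is Var(d) alone.

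- B: 66.7 + 0 + 0 = 66.7.
- C: 66.7 + 66.7 - 133.3 = 0.
- D: 0 + 66.7 + 0 = 66.7.

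Only in D, where the lesions start equal, does the score equal Var(d) for want of any baseline spread.

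**Does subtracting the NaF-1 score repair it?** No. The difference equals Var(d) + 2 Cov(b, d). It is 0 in B (no response) and also 0 in E (strongly discordant response: 66.7 - 66.7). In A, where every lesion halves, it is 16.7 - 66.7 = -50.

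**The case against.** The strongest reply is that this is a disclosed operational definition. The protocol says heterogeneity of response is determined by global SUV(hetero), prints the formula and says plainly that a higher score reflects more heterogeneous lesion activity; the SAP follows it. That stands: nothing is hidden, and protocol and SAP agree on this endpoint. What remains is a mismatch between the quantity defined and the objective it serves.

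Second, the consequence is limited. There is no formal hypothesis and the output is descriptive. That also stands, and it restricts the point to interpretation.

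Third, a reader might infer that the trial plans no analysis of lesion or heterogeneity change. The documents do not support that. Other endpoints are redacted; SAP sections 5.2.8 and 5.2.9 set out change-from-baseline models, and the Appendix 4 footnote abbreviates change and baseline. A suitable measure may already exist there, but it would not alter the secondary endpoint as written.

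Fourth, a reader might infer that the score carries no information on response. That is too strong: case D shows that it tracks the spread of change when lesions start alike. How far it departs in practice depends on baseline spread, which the documents do not give.

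Finally, requiring NaF-1 for inclusion may simply align the analysis set with the primary endpoint, so it is weak evidence of a defect.

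**Conclusion.** The point holds for the secondary endpoint as visibly defined. SUV(hetero) at NaF-3 is a valid description of heterogeneity of uptake at that scan. By itself it cannot separate heterogeneous response from heterogeneity already present at baseline, so it does not isolate the quantity in the secondary objective or in the design rationale.

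The size is shown by example only: 66.7 for unchanged lesions against 0 for lesions moving in opposite directions. These rest on assumed SUVmean values, matched lesions and constant volume. That the score contains no baseline term rests on no assumption. How many of the roughly 20 patients would be misdescribed cannot be estimated from the documents. No test, decision rule or sample size changes; the consequence is what the reported result can be said to show.

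**What to change.** In SAP sections 3.2 and 6.2:

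1. Relabel SUV(hetero) at NaF-3 as heterogeneity of uptake and present it beside its NaF-1 value. State that the difference between the two scores is also not a measure of response heterogeneity (cases B and E).
2. For the secondary objective, report per patient the lesion-level changes in SUV(total) from NaF-1 to NaF-3:
   - the percentage of baseline lesions responding by the primary endpoint's LOA rule, with a stated rule for resolved lesions;
   - the spread (SD or range) of change over matched lesions, on the scale of the vendor's LOA;
   - the numbers of resolved and new lesions.
3. If a redacted endpoint already provides item 2, name it as the measure for the secondary objective.

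The percentage should be described only as the mix of responder status, not as concordance. Lesions changing by +100%, +100% and 0% give 0%, and lesions changing by -50% and -95% give 100% at an assumed LOA of -20%, -30% or -40%. The spread is needed beside it, and the lesion counts beside both: with half the lesions resolved and half unchanged, the SD over matched lesions is 0.

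**Cost.** SAP wording and a small set of derivations. No scan is added and no patient is lost, since section 6.2 already requires both scans. Lesion-level SUV(total) change is needed for the primary endpoint anyway, but the documents do not say that lesion-level data reach the sponsor, so a transfer from the central vendor may be needed.

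**Downsides.** The percentage depends on the vendor's LOA: case C reads 33% at an assumed LOA of -20% or -30% and 0% at -40%. The spread needs matched lesions (at least two for an SD) and a rule for lesions that merge or split.
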